**Appendix A Schedule of Procedures – Every 4-Week Dosing *Continued***

	Screening f		Treatment Period												Follow-up Period		
	Run-in #	Qual *	1	1	5	9	13	17	21			22	23	25/ET	4*	8*	13*
Study Week	-5 to -1	-1 to 0	1	1	5	9	13	17	21			22	23	25/ET	4*	8*	13*
Study Day	-35 to -8	-7 to -1	1	2 a	29	57	85	113	141	142 a	143 a	148 a	155 a	169	* Weeks from the end of treatment period g		
Visit and Testing Window +/- Days	0	0	0	0	2	2	2	3	3	0	0	0	0	3	3	3	3
Liver Biomarkers			X				X		X					X			X
Plasma PK - ISIS 703802 l			X 	X 	X	X	X	X	X 	X 	X 	X	X	X	X	X	X
Anti-ISIS 703802 Antibodies			X		X	X	X		X					X	X		X
FSH (women only, if applicable) j, m	X																
Serum Pregnancy Test m	X		X		X	X	X	X	X					X	X	X	X
Archived Serum & Plasma Samples j, n			X			X		X	X					X	X	X	X
PD Panel and phospholipids j	X	X	X		X	X	X	X	X					X	X	X	X
Extended Lipid Panel j	X	X	X		X	X	X	X	X					X	X	X	X
HbA1C j	X		X				X							X			X
FPG, and delipidated free glycerol, insulin j	X		X		X	X	X	X	X					X	X	X	X
Biomarkers of Inflammation			X				X							X			X
Study Drug: SC Injection			EVERY 4-WEEK SUBCUTANEOUS ADMINISTRATION OF STUDY DRUG (Week 1 through Week 21/Day 141) o														
Adverse Events	X		X	X	X	X	X	X	X	X	X	X	X	X	X	X	X
Concomitant Medication	X		X	X	X	X	X	X	X	X	X	X	X	X	X	X	X

†Qual =Qualification

# Subjects on stable diet known to the investigator and followed at the site may go from Screening to qualification without the diet run-in period.

## Appendix A Schedule of Procedures – Every 4-Week Dosing *Continued*

All procedures and study samples are to be done pre-dose at respective visits, unless specified

- a Visit only required for subjects in PK subgroup.
- b Full physical exam will be performed at the Screening visit and an abbreviated physical exam will be performed during treatment and follow-up periods.
- c Height only required at Screening.
- d MRI will only be performed during Screening after all other eligibility criteria are met. MRI should be performed 10 days (+/- 2 days) prior to anticipated Day 1 date to allow time for result reporting and analysis
- e All tests listed in [Appendix B](#) under Extended Urinalysis should be performed, including routine urinalysis, urine microscopy, UACR and UPCR.
- f Assessments and procedures to be conducted by either a home healthcare service or the Study Center. Subject Study Center visits must be no more than 4 weeks apart during the treatment period
- g Urine samples for renal biomarkers will be collected. Sample analysis will be conducted in accordance with Safety Monitoring for Renal Function ([Section 8.5.2](#)).
- h During the follow-up period, hematology sampling for platelet values should continue to be taken every 14 days (+/- 2 days) for 6 weeks after Week 27/EOT, then at Week 4, Week 8, and Week 13 Follow-up visits.
- i Serum Creatinine and Cys-C will be collected as a part of chemistry panel at visits when chemistry panel is performed, or as stand-alone samples at time points when a chemistry panel is not performed.
- j Blood samples to be collected after an overnight fast of at least 10 hours and preferably not more than 12 hours, unless tests are repeated for safety reasons.
- k If the platelet value, serum creatinine or liver enzyme tests are uninterpretable (e.g., due to clumping, hemolysis or quantity not sufficient) a repeat blood specimen should be re-drawn as soon as possible (ideally within 7 days). All platelet count results will be reviewed promptly (within 48 hours of receipt) by the Investigator as per [Section 6.2.1](#). Any case of a platelet count  $\leq 50,000/\text{mm}^3$  should be reported in an expedited fashion to the Sponsor.
- l Refer to [Appendix C](#) for PK Sampling schedule.
- m Women who are not surgically sterile or post-menopausal.
- n Serum and plasma samples will be collected and stored for follow-up exploration of laboratory findings and/or AEs (e.g., measurement of cytokine and/or chemokine levels, measurement of additional markers of kidney function, measurement of antibodies, etc.) and will be retained until completion of the final study report.
- o Last dose of Study Drug will be administered at Week 21/Day 141 +/- 3 days.
- p Ultrasound to determine positive liver fat at screening will only be performed on patients who do not have a documented history of hepatic steatosis as determined by imaging (CT scan, MRI or US). Ultrasound may be repeated at the discretion of the PI. Results of Ultrasound must be available and confirm eligibility prior to MRI being performed.
- q Treatment period is defined as the time from the first dose through one dosing interval post last dose.
- r If a subject was screened and failed to meet eligibility under a previous protocol, the subject may be screened under the current protocol.
- s If a subject was screened and had an MRI, but failed to meet eligibility under a previous protocol, the MRI during rescreening may not need to be repeated. The need to repeat an MRI for such subjects should be discussed with the Medical Monitor.

### Time (time is in reference to Study Drug administration):

- 1 24-hr from previous dose of Study Drug
- 2 48-hr from previous dose of Study Drug
- 3 Pre-dose for all subjects and pre-dose, 1, 2, 4, 8 hours post SC injection for subjects on PK subgroup

## **Appendix B List of Laboratory Analytes**

## Appendix B List of Laboratory Analytes

Clinical Chemistry Panel	Screening Tests	Hematology	Extended Urinalysis

 
• Sodium
 
• Potassium
 
• Chloride
 
• Bicarbonate
 
• Total protein
 
• Albumin
 
• Calcium
 
• Magnesium
 
• Phosphorus
 
• Glucose
 
• BUN
 
• Creatinine
 
• Cholesterol
 
• Uric Acid
 
• Total bilirubin
 
• Direct (conjugated) bilirubin
 
• Indirect (unconjugated) bilirubin
 
• ALT
 
• AST
 
• Alkaline phosphatase
 
• Creatinine kinase
 
• GGT
 
• Cys-C
 
	
 
• Hepatitis B surface antigen
 
• Hepatitis C antibody
 
• HIV antibody
 
• FSH (women only)
 
• Serum <math>\beta</math>hCG
 
• TSH
 
• Free T4
 
• Free T3
 
 
Coagulation
 
 
• aPTT (sec)
 
• PT (sec)
 
• INR
 
 
Extended Lipid Panel
 
 
• Total Cholesterol (TC)
 
• LDL cholesterol (LDL-C)
 
• HDL cholesterol (HDL-C)
 
• Non-HDL cholesterol (non-HDL-C)
 
• Triglycerides (TG)
 
• VLDL cholesterol (VLDL-C)
 
• Lp(a)
 
• FFA
 
• ApoB-48
 
• ApoB-100
 
• ApoB
 
• ApoCIII
 
• Apo A-1
 
	
 
• Red blood cells
 
• Hemoglobin
 
• Hematocrit
 
• MCV, MCH, MCHC
 
• Platelets
 
• White blood cells
 
• WBC Differential (% and absolute) 
 
• Neutrophils
 
• Eosinophils
 
• Basophils
 
• Lymphocytes
 
• Monocytes
 
 
 
 
Pharmacokinetics
 
 
• ISIS 703802 levels in plasma
 
 
Immunogenicity
 
 
• Anti-ISIS 703802 antibodies
 
 
Liver Biomarkers (apoptosis and fibrosis)
 
 
• CK18
 
• PIINP
 
 
Inflammatory
 
 
• hs-CRP
 
• IL-6
 
• IFN gamma
 
• TNF alpha
 
• Leptin
 
• Adiponectin
 
	
 
• Routine Urinalysis 
 
- Color
 
- Appearance
 
- Specific gravity
 
- pH
 
- Protein
 
- Red Blood Cells
 
- Glucose
 
- Ketones
 
- Bilirubin
 
- Urobilinogen
 
- Leukocyte esterase
 
- Nitrate
 
 
 
• Microscopic examination
 
• P/C Ratio (UPCR)
 
• A/C Ratio (UACR)
 
 
Renal Urine Biomarkers
 
 
• NGAL
 
• NAG
 
• KIM-1
 
 
24-Hour Urine Test
 
 
• Creatinine clearance
 
• Protein
 
• Albumin
 
 
Phospholipids
 
 
• Ceramides
 
• Sphingolipids
 
• Diacylglycerol
 


PD Panel
 
 
• ANGPTL3
 
• Insulin
 
• Proinsulin
 
• C-peptide
 
• Fructosamine
 
• Glycated albumin
 
• Delipidated Free Glycerol
 
• Fasting Plasma Glucose
 
			

- 1 Plasma PK samples may also be used for profiling of drug binding proteins, bioanalytical method validation purposes, stability assessments, metabolite assessments, or to assess other actions of ISIS 703802 with plasma constituents
- 2 All samples will be collected, handled and stored under the conditions specified for the assays. Please refer to the study Laboratory Manual for details on the appropriate handling and storage methods for biomarker and other samples.

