#### 4.4 Unblinding of Treatment Assignment

All subjects, monitors, and Study Center personnel related to the study will be blinded throughout the study and until all subjects have completed the study and the database has been locked. The Sponsor will be blinded throughout the study and until all subjects have completed the treatment period. However, if a subject has suffered a SAE (as defined in [Section 9.3.3](#)), and/or when knowledge of the treatment assignment will impact the clinical management of the subject, the Investigator will have the ability to unblind the treatment assignment for that subject using the IXRS. The Sponsor will determine the point at which all treatment assignments will be unblinded. The Sponsor or designee will be informed of the unblinding of a subject within 24 hours. In addition, all SUSARs will be unblinded by the Sponsor's or designee's Drug Safety and Quality Assurance personnel for the purpose of regulatory reporting (see [Section 9.2](#)).

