## 9.5 Procedures for Handling Special Situations

### 9.5.1 *Abnormalities of Laboratory Tests*

Clinically significant abnormal laboratory test results may, in the opinion of the Investigator, constitute or be associated with an AE. Examples of these include abnormal laboratory results that are associated with symptoms, or require treatment, e.g., bleeding due to thrombocytopenia, tetany due to hypocalcemia, or cardiac arrhythmias due to hyperkalemia. Whenever possible, the underlying diagnosis should be listed in preference to abnormal laboratory values as AEs. Clinically significant abnormalities will be monitored by the Investigator until the parameter returns to its Baseline value or until agreement is reached between the Investigator and Sponsor Medical Monitor. Laboratory abnormalities deemed not clinically significant (NCS) by the Investigator should not be reported as AEs. Similarly, laboratory abnormalities reported as AEs by the Investigator should not be deemed NCS on the laboratory sheet.

The Investigator is responsible for reviewing and signing all laboratory reports. The signed clinical laboratory reports will serve as source documents and should include the Investigator's assessment of clinical significance of out of range/abnormal laboratory values.

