**Appendix A Schedule of Procedures – Weekly Dosing**

Study Week	Screening r		Treatment Period												Follow-up Period			
	Run-in #	Qual †	1	1	5	9	13	17	21	25	26			27/ET	4*	8*	13*	
Study Day	-5 to -1	-1 to 0	1	2 a	29	57	85	113	141	169	176	177 a	178 a	183	*Weeks from the end of treatment period q			
Visit and Testing Window +/- Days	0	0	0	0	2	2	2	3	3	3	3	0	0	3	3	3	3	
Informed Consent	X																	
Outpatient Visit	X	X	X	X	X	X	X	X	X	X	X	X	X	X	X	X	X	
Inclusion/Exclusion Criteria	X	X	X															
Medical History	X																	
Vital Signs	X		X		X	X	X	X	X	X	X			X	X	X	X	
Physical Examination b	X		X		X		X							X	X	X	X	
Waist circumference/ WHR			X				X							X				
Body Weight and Height c	X	X	X		X	X	X	X	X	X	X			X	X	X	X	
12- lead ECG (triplicate)	X		X		X		X		X					X	X	X	X	
Ultrasound p	X																	
MRI		X d, s					X							X				
24-Hour Urine for Creatinine Clearance and Protein		X																
Extended Urinalysis e	X		EVERY 14 DAYS (+/- 2 days) e, f					X	X	X				X	X	X	X	
Renal Biomarkers g	X		EVERY 14 DAYS (+/- 2 days) f, g					X	X	X				X	X h	X h	X h	
Serum Creatinine and Cys-C i, j, k	X		EVERY 14 DAYS (+/- 2 days) f, i					X	X	X				X	X	X	X	
Chemistry Panel j, k	X		EVERY 14 DAYS (+/- 2 days) f					X	X	X				X	X	X	X	
Hematology j, k	X		X	HEMATOLOGY PERFORMED EVERY 14 DAYS (+/- 2 days) f, k												X h	X h	X h
Coagulation	X		X				X							X			X	
Hepatitis B, C, HIV	X																	
Thyroid Panel	X																	

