**Appendix A Schedule of Procedures – Every 4-Week Dosing**

	Screening f		Treatment Period												Follow-up Period			
	Run-in#	Qual †	1	1	5	9	13	17	21		22	23	25/ET	4*	8*	13*		
Study Week	-5 to -1	-1 to 0	1	1	5	9	13	17	21		22	23	25/ET	4*	8*	13*		
Study Day	-35 to -8	-7 to -1	1	2 a	29	57	85	113	141	142 a	143 a	148 a	155 a	169	* Weeks from the end of treatment period q			
Visit and Testing Window +/- Days	0	0	0	0	2	2	2	3	3	0	0	0	0	3	3	3		
Informed Consent	X																	
Outpatient Visit	X	X	X	X	X	X	X	X	X	X	X	X	X	X	X	X		
Inclusion/Exclusion Criteria	X	X	X															
Medical History	X																	
Vital Signs	X		X		X	X	X	X	X			X		X	X	X		
Physical Examination b	X		X		X		X							X	X	X		
Waist circumference/ WHR			X				X							X				
Body Weight and Height c	X	X	X		X	X	X	X	X					X	X	X		
12- lead ECG (triplicate)	X		X		X		X		X					X	X	X		
Ultrasound p	X																	
MRI	X d, s						X							X				
24-Hour Urine for Creatinine Clearance and Protein		X																
Extended Urinalysis e	X		EVERY 14 DAYS (+/- 2 days) e, f					X	X					X	X	X	X	
Renal Biomarkers g	X		EVERY 14 DAYS (+/- 2 days) f, g					X	X					X	X h	X h	X h	
Serum Creatinine and Cys-C i, j, k	X		EVERY 14 DAYS (+/- 2 days) f, i					X	X					X	X	X	X	
Chemistry Panel l, k	X		EVERY 14 DAYS f					X	X					X	X	X	X	
Hematology j, k	X		X	HEMATOLOGY PERFORMED EVERY 14 DAYS (+/- 2 days) f, k												X h	X h	X h
Coagulation	X		X				X							X		X		
Hepatitis B, C, HIV	X																	
Thyroid Panel	X																	

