2.4 Data Monitoring

In order to ensure maintenance of the study blind, following randomization the results of efficacy parameters consisting of lipid panel results including apoA-I, apoB (100, 48), apoC-III, TC, FFA, LDL-C, HDL-C, non-HDL-C, VLDL-C, triglycerides and Lp(a), PK and selected PD panel results, ANGPTL3 and MRIs will be blinded to the Akcea study team, Clinical Research Organization (CRO) study team, Investigators, Study Center personnel and patients until after database lock for EoT. After Sponsor's unblinding post completion of treatment period, blinded study personnel will continue to oversee the study until all patients completed the study.

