2.5.2 Laboratory Data

The Sponsor is responsible for the format of the laboratory electronic data transfers and the transfer schedule. The Sponsor (or designee) is responsible for the review of the clinical laboratory data. Central lab data are not stored in the EDC system but will be transferred to Trennic Data Services.

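### Does the second cholesterol listing, in the chemistry panel, undo the masking of total cholesterol?

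*Protocol*

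**What the plan says.** SAP 2.4 (Data Monitoring) lists what is withheld after randomisation in order to protect the blind. The list opens with "the results of efficacy parameters consisting of lipid panel results including apoA-I, apoB (100, 48), apoC-III, TC", continues through the other lipids, and adds PK, selected PD results, ANGPTL3 and MRI. These are to be "blinded to the Akcea study team, Clinical Research Organization (CRO) study team, Investigators, Study Center personnel and patients until after database lock" for the end of treatment. The chemistry panel is not mentioned.

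Protocol Appendix B lists TC in the Extended Lipid Panel. It also lists cholesterol in the Clinical Chemistry Panel: "Creatinine • Cholesterol • Uric Acid".

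On access to results, Protocol 9.5.1 states: "The Investigator is responsible for reviewing and signing all laboratory reports". SAP 2.5.2 states: "The Sponsor (or designee) is responsible for the review of the clinical laboratory data". Protocol 4.4 sets out which people are blinded and for how long (for the sponsor, "The Sponsor will be blinded throughout the study and until all subjects have completed the treatment period") but names no analyte.

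**The concern.** The masking sentence is built around the lipid panel, and the same analyte also sits in a panel it does not mention. A laboratory that suppressed results by panel could follow the sentence to the letter and still print cholesterol on every chemistry report. The investigator signs those reports, and the sponsor or its designee reviews the data.

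TC is a secondary efficacy endpoint that the drug is expected to lower, so a run of falling values could hint at the assignment. What would be exposed is judgement: attribution of adverse events, discretionary withdrawal under Protocol 8.9 and, if the sponsor saw the values, the decisions on major deviations that define the Per Protocol Set before unblinding.

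**Working it through.** The documents give no figure to reproduce. The check counts the values at issue, asks whether they add to the lipid panel, and then compares the texts.

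**Values per patient.** The chemistry row of Protocol Appendix A reads "EVERY 14 DAYS (+/- 2 days) f" for weekly dosing and "EVERY 14 DAYS f" for dosing every 4 weeks. In both, this runs to Week 13 and is followed by named visits.

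- Days 15, 29, 43, 57, 71 and 85: 6 draws.
- Cohort A adds Weeks 17, 21, 25 and 27: 6 + 4 = 10.
- Cohorts B and C add Weeks 17, 21 and 25: 6 + 3 = 9.
- Across the planned 32 and 64 patients: 32 × 10 + 64 × 9 = 320 + 576 = 896 panels, if all are completed.

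**Overlap with the lipid panel.** After Day 1 the Extended Lipid Panel is scheduled on Days 29, 57, 85, 113 and 141. Cohort A adds Days 176 and 183; Cohorts B and C add Day 169. Chemistry is therefore drawn without a lipid panel on Days 15, 43 and 71 in every cohort, and on Day 169 in Cohort A. The chemistry cholesterol is not merely a second printing of a masked result.

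**Which reading fits the texts.**

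- SAP 2.4 gives maintenance of the blind as its purpose and names TC individually. Releasing TC because another panel reported it would defeat that purpose.
- SAP 3.5.2 repeats the chemistry panel for analysis but leaves out two of the Appendix B items, cholesterol and glucose. These are the two that also have a place in the lipid and PD panels. The omission is not a masking instruction, but it fits treating cholesterol as an efficacy analyte.
- The duty to sign all laboratory reports applies equally to lipid reports. If it implied that chemistry cholesterol is visible, it would imply the same for triglycerides and LDL-C, which SAP 2.4 expressly masks. It must mean reports as issued to the site.
- No monitoring or stopping rule in Protocol 8.5 and 8.6 uses cholesterol, so nothing in safety management requires its release.

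**How revealing the values would be.** Protocol 2.3.4.1 gives the only TC effect: group-mean reductions up to 28%, for the unconjugated parent drug at other doses, with no placebo figure. The nearest evidence for ISIS 703802 is non-HDL-C in Protocol 2.3.4, with reductions of 10.0% to 36.6% against 9.1% on placebo. The contrast is 10.0 − 9.1 = 0.9 points at one end and 36.6 − 9.1 = 27.5 points at the other, over 10 to 60 mg weekly. Protocol 2.4 puts this trial's exposures at the equivalent of 10 to 20 mg weekly, and values by dose are not given. Without a between-patient SD for TC, no probability of guessing the arm can be supported.

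**The case for a change.** The best case for acting is that the wording really is open. TC is introduced as a lipid panel result, Appendix B lists cholesterol twice, and three or four of the on-treatment chemistry draws have no lipid panel beside them. The sponsor itself classed TC as a result to hide, and one sentence would cost almost nothing.

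The facts in that case stand, as does the point that neither document settles the chemistry value in terms. The remedy is weaker. The SAP took effect on 12 December 2019 and describes a trial already being conducted under a protocol amendment of March 2019. A sentence added to it instructs neither the laboratory nor the sites and cannot recall reports already issued. The operative control is the central laboratory's report configuration, which is outside these documents and may already suppress the value. Checking it is routine trial conduct and does not depend on a revised plan.

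**Conclusion.** The plan has not written down how a duplicated analyte is handled. The sponsor and the laboratory would ordinarily fill that gap in the report set-up. On the natural reading of SAP 2.4 cholesterol is masked from any source, and following the plan that way leaves its results and conclusions sound.

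If masking were instead applied panel by panel, 9 or 10 on-treatment values per patient would be visible, with an information content the documents do not let us measure. Even then the effect on the main result would be limited: the primary endpoint is a central-laboratory triglyceride value analysed in the Full Analysis Set, and the Per Protocol Set is supportive only. What would remain is a possible influence on adverse event attribution and discretionary withdrawal.

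The conclusion assumes that the laboratory masks by analyte, as the purpose of SAP 2.4 implies. Nothing in the documents shows otherwise.

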**Appendix C    PK Sampling Schedule**  
Sampling Schedule for Weekly Dosing Cohort  
Sampling Schedule for Every 4-Week Dosing Cohorts

**Appendix C PK Sampling Schedule for Weekly Dosing Cohort**

	Treatment Period											Follow-up Period		
Study Week	1	1	5	9	13	17	21	26			27	4*	8*	13*
Study Day	1	2	29	57	85	113	141	176	177	178	183	*Weeks from the end of treatment period 		
All Subjects	Pre-dose	NA	Pre-dose	Pre-dose	Pre-dose	Pre-dose	Pre-dose	Pre-dose	NA	NA	Anytime	Anytime	Anytime	Anytime
PK Sub-group Only	Pre-dose, 1, 2, 4, & 8-hr 	24-hr 	Pre-dose	Pre-dose	Pre-dose	Pre-dose	Pre-dose	Pre-dose, 1, 2, 4, & 8-hr 	24-hr 	48-hr 	Anytime	Anytime	Anytime	Anytime

1 Window of (-) 2 hrs

2 24-hr from previous dose of Study Drug. Window of (+/-) 4 hours

3 48-hr from previous dose of Study Drug. Window of (+/-) 6 hours

4 Treatment period is defined as the time from the first dose through one dosing interval post last dose

**Appendix C PK Sampling Schedule for Every 4-Week Dosing Cohorts**

	Treatment Period												Follow-up Period		
Study Week	1	1	5	9	13	17	21			22	23	25	4*	8*	13*
Study Day	1	2	29	57	85	113	141	142	143	148	155	169	*Weeks from the end of treatment period 		
All Subjects	Pre-dose	NA	Pre-dose	Pre-dose	Pre-dose	Pre-dose	Pre-dose	NA	NA	NA	NA	Anytime	Anytime	Anytime	Anytime
PK Sub-group only	Pre-dose, 1, 2, 4, and 8-hr 	24-hr 	Pre-dose	Pre-dose	Pre-dose	Pre-dose	Pre-dose, 1, 2, 4, and 8-hr 	24-hr 	48-hr 	Anytime	Anytime	Anytime	Anytime	Anytime	Anytime

- 1 Window of (-) 2 hours allowed
- 2 24-hr from previous dose of Study Drug. Window of (+/-) 4 hours allowed
- 3 48-hr from previous dose of Study Drug. Window of (+/-) 6 hours allowed
- 4 Treatment period is defined as the time from the first dose through one dosing interval post last dose

## **Appendix D      Grading Scale for Adverse Events Relating to Laboratory Abnormalities**

## Appendix D Grading Scale for Adverse Events Relating to Laboratory Abnormalities

The following grading recommendations for adverse events relating to lab test abnormalities are based upon the Common Terminology Criteria for Adverse Events (CTCAE) Version 4.03, June 2010.

Adverse Event	Mild	Moderate	Severe
Hematology			
aPTT prolonged	>ULN - 1.5 x ULN	>1.5 - 2.5 x ULN	>2.5 x ULN; hemorrhage
Eosinophils increased f	650 – 1,500 cell/mm 	1,501 - 5,000 cell/mm 	>5,000 cell/mm 
Fibrinogen decreased	<1.0 - 0.75 x LLN or <25% decrease from baseline	<0.75 - 0.5 x LLN or 25 - <50% decrease from baseline	<0.5 x LLN or ≥50% decrease from baseline
Hemoglobin decreased (Anemia)	Hemoglobin (Hgb) <LLN - 10.0 g/dL; <LLN - 6.2 mmol/L; <LLN - 100 g/L	Hgb <10.0 - 8.0 g/dL; <6.2 - 4.9 mmol/L; <100 - 80g/L	Hgb <8.0 g/dL; <4.9 mmol/L; <80 g/L; transfusion indicated
Hemoglobin increased	Increase in >0 - 2 g/dL above ULN or above baseline if baseline is above ULN	Increase in >2 - 4 g/dL above ULN or above baseline if baseline is above ULN	Increase in >4 g/dL above ULN or above baseline if baseline is above ULN
INR increased	>1 - 1.5 x ULN; >1 - 1.5 times above baseline if on anticoagulation	>1.5 - 2.5 x ULN; >1.5 - 2.5 times above baseline if on anticoagulation	>2.5 x ULN; >2.5 times above baseline if on anticoagulation
Lymphocyte count decreased	<LLN - 800/mm  ; <LLN - 0.8 x 10  /L	<800 - 500/mm  ; <0.8 - 0.5 x 10  /L	<500 /mm  ; <0.5 x 10  /L
Lymphocyte count increased	-	>4000/mm  - 20,000/mm 	>20,000/mm 
Neutrophil count decreased	<LLN - 1500/mm  ; <LLN - 1.5 x 10  /L	<1500 - 1000/mm  ; <1.5 - 1.0 x 10  /L	<1000/mm  ; <1.0 x 10  /L
Platelet count decreased	<LLN - 75,000/mm  ; <LLN - 75.0 x 10  /L	<75,000 - 50,000/mm  ; <75.0 - 50.0 x 10  /L	<50,000/mm  ; <50.0 x 10  /L
White blood cell decreased	<LLN - 3000/mm  ; <LLN - 3.0 x 10  /L	<3000 - 2000/mm  ; <3.0 - 2.0 x 10  /L	<2000/mm  ; <2.0 x 10  /L
Chemistry			
Acidosis	pH <normal, but ≥7.3	-	pH <7.3
Alanine aminotransferase increased	>ULN - 3.0 x ULN	>3.0 - 5.0 x ULN	>5.0 x ULN
Alkaline phosphatase increased	>ULN - 2.5 x ULN	>2.5 - 5.0 x ULN	>5.0 x ULN
Alkalosis	pH >normal, but ≤7.5	-	pH >7.5
Aspartate aminotransferase increased	>ULN - 3.0 x ULN	>3.0 - 5.0 x ULN	>5.0 x ULN
Blood bilirubin increased	>ULN - 1.5 x ULN	>1.5 - 3.0 x ULN	>3.0 x ULN
Cardiac troponin I increased	Levels above the upper limit of normal and below the level of myocardial infarction as defined by the manufacturer	-	Levels consistent with myocardial infarction as defined by the manufacturer

